interventions.(35, 42) In addition, adding a functional warm-up program, has shown to reduce injuries by 40%.(43-46). RS also builds social capital and is associated with positive motivational factors.(47) The physiologic and behavioral aspects of RS associated with health improvements are summarized by the Football (soccer) is Medicine collaborative we belong to.(24)

Protocol Synopsis

Study Design: A randomized controlled trial to compare two lifestyle intervention deliveries and their effect on bone health and diet and physical activity related measures.

Planned Sample Size: 20 subjects

Subject population: Inclusion criteria: 1) Men aged 18-79 years; 2) PCa survivors that had at least 6 months of hormone therapy (i.e. ADT with testosterone lowering agents) within the past 10 years; 3) not engaged in soccer practice or other exercise or lifestyle intervention program for the past 12-months; 4) Availability of smartphone to receive text messages; 5) Treating Oncologist clearance 6) ability to read in English or Spanish and provide informed consent; **Exclusion criteria:** 1) BMI > 40 kg/m²; 2) resting BP ≥170/100 at screening or uncontrolled hypertension; 3) any mobility issues or exercise program contraindications (48); 4) a recent (i.e., within 12 months) myocardial infarction, diagnosis of congestive heart disease, other active cancer 5) bone or organ metastases, 6) chemotherapy within past 6 months; 7) Therapies and diseases of bone unrelated to PCa e.g. systemic glucocorticoids, bisphosphonates, teriparatide, denosumab, osteomalacia; osteosarcoma; Paget's disease; systemic lupus erythematosus; inflammatory bowel diseases, rheumatoid arthritis; thyroid/parathyroid disorder or mental illness.8) Not COVID-19 vaccinated

Specific Aims

Aim 1: We will conduct a single-arm clinical trial over 3 months, among PCa survivors that had at least 6 months of hormone therapy (i.e. ADT with testosterone lowering agents) within the past 10 years. Participants (n=20) will be offered an intensive intervention including RS programming and lifestyle education. The group will receive RS, consisting of small-sided (5vs5) conditioning drills and games, adapted to the population (60-minute sessions twice/week). We will evaluate pre vs post differences over 3-months in:

(Aim 1a): Primary outcome: lumbar spine BMD at 3-months.

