(Aim 1b): Secondary outcomes: impact on additional markers of bone health including total hip BMD and bone turnover markers (Osteocalcin (a marker of bone formation) and C-terminal telopeptide of collagen (CTX) a bone resorption marker), body composition (weight, BMI, % body fat, waist circumference, lean body mass), cardiometabolic markers (resting heart rate and blood pressure), functional markers (aerobic capacity, muscle strength), behavioral factors (diet and PA self-efficacy, dietary intake, smoking and alcohol habits, weekly steps, sedentary and sleep time) and patient-reported quality of life and depression symptoms.

Aim 2: To assess implementation feasibility and evaluate overall efficacy to increase engagement and adherence with PA, we will evaluate between-group differences over 3 months in:

(Aim 2a): compliance with recommendations of 150 minutes of moderate-to-vigorous PA/week.

(Aim 2b): To assess the RS program adherence and tolerance, we will monitor session attendance, attrition rates, injuries or adverse events, use surveys for assessing participant program satisfaction and behavior change self-efficacy

Research Design:

Organizational structure of study team: This study was investigator initiated and proposed to the Winship Cancer Institute prostate cancer funding opportunity at Emory University as part of an internal pilot grant. The funder's expectation was for the investigator to conduct feasibility or pilot research to support a larger grant. Funder will provide a speedtype for all expenses related to the study.

Setting: All assessments will be conducted at the Emory University Hospital Georgia CTSA GCRC location (baseline and post intervention). Those randomized to the soccer intervention will attend soccer sessions at a local soccer field (either Dunwoody Elementary or the Atlanta Silverbacks indoor facility), no permission is

needed to conduct the study, but field owners are aware of the study be conducted. All data will be collected on paper and transferred to a REDCap database at Emory University Rollins School of Public Health.

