Study Assessments. Prior to testing, subjects will be asked to refrain from physical activity for 48 hours prior to test day, refrain from alcohol 24 hour prior to testing, and refrain from caffeinated drinks, smoking and other stimulants one hour prior to testing. Assessments will be conducted at baseline and post intervention at the Emory University Hospital Georgia CTSA research center (GCRC). Blood pressure, both systolic and diastolic blood pressure will be measured while sitting using a calibrated electronic blood pressure sphygmomanometer prior to any activity and after five minutes of rest., height and weight, waist circumference, aerobic and musculoskeletal fitness assessments will be performed. Bone mineral density will be measured by dual x-ray absorptiometry (DXA) scan at the lumbar spine (L2-L4) and total hip. Body composition will also be determined by DXA scan in the Bionutrition Unit of the GCRC. Venipuncture will be performed by the research nurse for bone turnover markers (Osteocalcin (a marker of bone formation) and C-terminal telopeptide of collagen (CTX) a bone resorption marker), a total testosterone level if not included in a recent clinic visit, and to bank one tube of plasma for future metabolomics studies. In addition, questionnaires will be used for self-reported physical and mental health, quality of life, PA and diet self-efficacy, program satisfaction and injuries. Dietary recalls will be conducted at baseline and 26 weeks by trained staff and analyzed using Nutrition Database System for Research.(49) In addition, both groups will also be asked to wear a Garmin fitness tracker for the duration of the study to measure steps and moderate and vigorous activity. Once baseline measurements are complete and 20 participants have completed they will be randomized to either the soccer group or the mobile health (mHealth) group. Participants in the soccer group will participate in soccer drills and other fitness routines (two 1-hour sessions per week). They will meet with the soccer coach after the soccer sessions to discuss the lifestyle education topics (Life's Simple 7 education topics). During the soccer sessions participants will be fitted with a wearable soccer-specific device to measure how much they move and their heart rate.

Informed Consent Process:

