Participants will receive a \$20 gift card for each assessment visit plus a parking voucher (total compensation value \$52). Subjects that complete the study will be allowed to keep the Garmin fitness tracker.

Data Analytics and Statistical Plan:

Descriptive analysis will be performed to assess the study primary aims. All statistical tests will be 2-sided, and the significance level will be set at 0.05. Data will be assessed for normality and reviewed for outliers and missing values. Mathematical transformations may be applied to meet normality assumptions. All primary analyses will be performed using the intention-to-treat principle to estimate the effects of the program.

Moreover, we will estimate the intervention efficacy using as-treated analysis, where participants are classified according to the number of sessions actually attended (i.e. the dose-response will be evaluated). To assess the effect of the proposed intervention program between baseline and 3 months, to compare the differences in the changes of the primary outcome of BMD and secondary outcomes, multilevel longitudinal models (MLM) will be used to test for differences time effects while adjusting for attrition and the correlational structure within time (repeated measures). Potential covariates may include potential effects of age, smoking, alcohol use, and therapy type. Attention will also be paid to heterogeneity between subjects (random intercept effects). Given the sample size of 40 subjects, only large effect sizes will be detectable at 80% statistical power. However, the primary focus of the analysis will be to gather initial estimates on the effect sizes (group differences and intervention efficacy) to establish adequate statistical power for a future larger study. **All analysis will be conducted by [name].**

Training of study team:

As stated above all staff and soccer coaches will receive adequate training of all study procedures. All study staff and collaborators will take CITI training upon hire.

Confidentiality: All participants will receive a study ID and this will be used on all paper and electronic forms. We will destroy all identifiers and any audio from key interviews after the study is complete.

References

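### Aim 2a judges activity only against the 150-minute threshold; add the tracker's moderate-to-vigorous minutes as a continuous outcome

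*Combined protocol and SAP*

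**What the plan says.** Under Specific Aims, Aim 2 states that "we will evaluate between-group differences over 3 months in" two items. The activity item, Aim 2a, is "compliance with recommendations of 150 minutes of moderate-to-vigorous PA/week". It does not say whether compliance is judged week by week, on the three-month average or once at the end. It does not name the data source or say how vigorous minutes count.

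Study Assessments asks both groups to "wear a Garmin fitness tracker for the duration of the study to measure steps and moderate and vigorous activity". The activity measures listed in Aim 1b are "weekly steps, sedentary and sleep time"; moderate-to-vigorous minutes appear in no aim.

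The Data Analytics and Statistical Plan describes a multilevel longitudinal model for BMD and the secondary outcomes between baseline and 3 months. It permits transformations and a general review of outliers and missing values, and it makes effect-size estimation for a later trial the main purpose. It does not mention Aim 2a, weekly tracker values or a wear-time rule.

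The design and size are stated inconsistently. Aim 1 says "We will conduct a single-arm clinical trial over 3 months", while Study Assessments says "they will be randomized to either the soccer group or the mobile health (mHealth) group". The Protocol Synopsis gives "Planned Sample Size: 20 subjects", while the statistical plan writes "Given the sample size of 40 subjects".

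**The concern.** Cutting a measured quantity at a threshold treats 20 and 140 minutes as the same failure, and 150 and 300 as the same success. In a pilot with 10 or 20 men per arm, whose stated product is an effect-size estimate, that loss matters. A difference in weekly minutes with a confidence interval can be carried straight into the design of the next trial; a compliance proportion from so few men is much less informative.

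The threshold also sits close to what the intervention supplies. Full attendance gives 2 × 60 = 120 minutes a week, which is 120/150 = 80% of the target. Many soccer participants may therefore fall near the cut, where an unstated scoring rule could decide who complies.

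**Working it through.** **1. The plan's own figure.** The statistical plan says that 40 subjects can detect only large effects at 80% power, two-sided 0.05. Assuming 1:1 allocation, d = (1.96 + 0.84) × √(2/n per arm).
- 20 per arm: 2.80 × √(2/20) = 0.89 (0.91 by the noncentral t).
- 10 per arm: 2.80 × √(2/10) = 1.25 (1.32 by the noncentral t).

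The first is consistent with the plan's wording if large means d of at least 0.8. The statement is general, gives no SD or rate, and makes no claim about Aim 2a.

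**2. Minutes against compliance, normal model.** The documents give no activity means or SDs, so every input here is assumed:
- 13 weekly values per man;
- normal between-person variation, SD 40 to 80 minutes;
- within-person weekly SD of 40 or 60 minutes;
- weeks truncated at zero;
- group means from 30 vs 120 to 90 vs 210 minutes;
- 16 scenarios, 20,000 runs each.

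Yes/no means that a man's average is at least 150. The mid-range example is 60 vs 150 minutes, SD 80, weekly SD 60.

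| Power | Minutes (t) | Share of weeks met (t) | Yes/no per man (Fisher) |
|---|---|---|---|
| Mid-range, 10 per arm | 63% | 57% | 22% |
| Mid-range, 20 per arm | 92% | 87% | 62% |
| All 16, 10 per arm | 53–100% | 42–96% | 6–51% |
| All 16, 20 per arm | 84–100% | 73–100% | 38–91% |

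Share of weeks is 3 to 17 points below minutes at 10 per arm (median 6), and 0 to 12 points below at 20 per arm (median 2).

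**3. Consequence for a follow-on trial, same model.** Men per arm for 80% power = 2 × (2.80/d)². In the mid-range example d is 1.09, 1.03 and 0.85 for the three measures.
- Minutes: 2 × (2.80/1.09)² = 13.2.
- Share of weeks: 2 × (2.80/1.03)² = 14.8, a ratio of (1.09/1.03)² = 1.12.
- Yes/no: 2 × (2.80/0.85)² = 21.7, a ratio of (1.09/0.85)² = 1.64.

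Across the scenarios the ratio is 1.01 to 2.5 for share of weeks (median 1.18) and 1.4 to 8.2 for yes/no (median 1.75).

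**4. Skewed minutes.** With right-skewed (lognormal) minutes, also assumed, the ranking against share of weeks can reverse.
- 90 vs 210 minutes, between-person coefficient of variation 1, 10 per arm: about 42% for raw minutes, 47% for share of weeks.
- A skewed baseline with mean 90, plus two 60-minute sessions at 90% attendance: 78% vs 92% at 10 per arm; 93% vs 99.8% at 20.

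Of 14 skewed scenarios at 10 per arm, share of weeks beat raw minutes in 7. Log-transformed minutes beat share of weeks in all 14. Raw minutes beat the once-per-man yes/no in every skewed case where the two were compared.

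**5. Missing weeks.** Assume 90 vs 120 minutes, SD 60, weekly SD 40, and non-wear in 30% vs 10% of weeks. Before truncation, excluding those weeks gives 120 − 90 = 30 minutes; counting them as zero gives 0.9 × 120 − 0.7 × 90 = 45. With weeks truncated at zero the simulated values are as follows.

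| Outcome | Non-wear excluded | Counted as zero | Change |
|---|---|---|---|
| Minutes | 27.7 | 43.6 | 43.6/27.7 = 1.57, up 57% |
| Share of weeks (points) | 13.6 | 16.3 | 16.3/13.6 = 1.20, up 20% |

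**6. Vigorous minutes.** If every session minute counts once, full attendance leaves 150 − 120 = 30 minutes to find elsewhere. If vigorous minutes counted double (assumption), the same sessions could score up to 240.

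**The case against.** The strongest reply is that compliance is the right measure for this aim. Aim 2 is about feasibility and adherence, and meeting the guideline is a direct adherence measure. That stands, and it is why compliance should be kept.

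A reader might infer that minutes always beat compliance. They do not: step 4 shows share of weeks ahead of untransformed minutes under plausible skew, and step 5 shows minutes to be the more sensitive, in relative terms, to how non-wear is handled. A transformation provision and a wear-time rule are therefore part of the recommendation.

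A reader might also infer that the plan intends one yes/no per man, the reading that produces the largest losses. The documents do not say so, and a per-week target can fairly be read as share of weeks. Part of the yes/no gap also comes from Fisher's test, which the plan never names. With a true difference of 0.9 SD, 20 per arm and the cut midway between the group means, Fisher gives 46% and the normal approximation 60%; the continuous outcome gives 79%.

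Finally, the plan is not blind to continuous activity. Weekly steps are in Aim 1b, the model for secondary outcomes might be taken to extend to Aim 2a, and nothing forbids reporting minutes. But steps do not measure the intensity that Aim 2a concerns, and an outcome named nowhere leaves its definition and scale to be chosen after the data are seen.

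**Conclusion.** The point holds as a cheap improvement. Aim 2a leaves out a continuous measure that the tracker is already set to record in both groups, and adding it serves the plan's stated purpose.

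The gain is clear against a once-per-man yes/no. Against share of weeks it is modest under the normal model, and it is not assured for raw minutes if they are skewed. All sizes depend on assumed means, SDs, skew and non-wear rates.

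A reader might conclude that Aim 2a is underpowered or that the plan miscalculated. Neither follows, since the plan claims no power for this aim. The absence of scoring and wear-time rules would by itself be only missing detail; the substance is the unlisted continuous outcome. A between-group estimate also presupposes two groups, so it falls away if the single-arm description is the true one.

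**What to change.** 1. First reconcile the single-arm and randomised descriptions, and 20 versus 40 subjects.
2. Add mean weekly moderate-to-vigorous minutes from the tracker as a continuous Aim 2a outcome. Report the between-group difference with a 95% CI, analyse on a log or similar scale if the minutes are skewed, and state how weeks with zero minutes enter that scale.
3. State that the weekly values enter the multilevel model already described in the statistical plan.
4. Keep guideline compliance, scored as the share of valid weeks at or above 150 minutes.
5. Before any outcome data are seen, fix one rule for both outcomes covering what makes a week valid, how non-wear is handled and how vigorous minutes count. Use the same device as the source in both groups.

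Under the randomised design the cost is SAP wording, one more outcome with its wear-time rules, and a short analysis, with no new data collection. If the trial is single-arm, a change in minutes would measure the increase in activity only if there is a tracker period before the intervention; none is stated, so one would have to be added.

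### Dietary intake is to be analysed as a change from baseline to 3 months, but its only follow-up recall is scheduled at 26 weeks

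*Combined protocol and SAP*

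**What the plan says.** Four parts of the combined protocol and SAP bear on this.

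- **Specific Aims, Aim 1.** The trial runs for 3 months, and Aims 1a and 1b sit under the lead-in "We will evaluate pre vs post differences over 3-months in". The behavioural outcomes in Aim 1b include "diet and PA self-efficacy, dietary intake, smoking and alcohol habits". Dietary intake is therefore an outcome in its own right, separate from diet self-efficacy.
- **Data Analytics and Statistical Plan.** The multilevel models for the primary and secondary outcomes are introduced with "To assess the effect of the proposed intervention program between baseline and 3 months". No later analysis time is given.
- **Study Assessments.** The general rule is "Assessments will be conducted at baseline and post intervention at the Emory University Hospital Georgia CTSA research center". The Setting paragraph under Research Design gives the same two occasions. For diet alone, Study Assessments then sets its own time: "Dietary recalls will be conducted at baseline and 26 weeks by trained staff".
- **Compensation.** Participants receive a $20 "gift card for each assessment visit plus a parking voucher", with a stated total value of $52.

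**The concern.** The time at which dietary intake is collected is not the time at which it is analysed. Someone following the recall sentence would collect intake at baseline and at about 6 months, and nothing at the 3-month point that the aims and the model call for.

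Putting the 26-week value in the 3-month slot would not repair this. The trial lasts 3 months, so a recall at 26 weeks reflects whatever persists of the programme's effect together with behaviour after it ended. The two cannot be separated without a value at the end of the programme. Treating time as continuous does not help either: with only these two time points, a straight-line model would assign to 3 months about half of the 26-week change, and the data could not test that assumption.

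The plan says that "the primary focus of the analysis will be to gather initial estimates on the effect sizes" for a larger study. A mistimed dietary estimate could enter that planning if dietary intake is used there. There is also a practical risk. Staff who notice the conflict may settle it differently, so that some recalls are taken near week 13 and others near week 26. A recall describes intake around the time it is taken, so a missed time point cannot be recovered later.

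**Working it through.** **Inputs**

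| Item | Value | Where |
|---|---|---|
| Trial and pre/post comparison period | 3 months | Specific Aims, Aim 1 |
| Analysis period for primary and secondary outcomes | baseline to 3 months | Data Analytics and Statistical Plan |
| Dietary recall times | baseline, 26 weeks | Study Assessments |
| Assessment occasions in general | baseline, post intervention | Research Design (Setting); Study Assessments |
| Payment | $20 per assessment visit plus parking; total $52 | Compensation |
| Sample size | 20, or 40 | 20 in the Protocol Synopsis and Aim 1; 40 in the statistical plan |

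**Step 1: put the times on one scale.**
3 months = 3 × (365.25 / 12) / 7 = 13.04 weeks.
26 weeks = 26 × 7 / (365.25 / 12) = 5.98 months.
Gap = 26 − 13.04 = 12.96 weeks, about 13 weeks.
Ratio = 26 / 13.04 = 1.99, about 2.

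**Step 2: count usable dietary time points.** Two recall times are listed. Only baseline lies in the window from 0 to 13 weeks. A change score needs two values in the window, so the number of participants with a 3-month dietary change is 0 out of 20, or 0 out of 40.

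**Step 3: look for another source of intake data.** The questionnaires in Study Assessments cover physical and mental health, quality of life, physical activity and diet self-efficacy, satisfaction and injuries. Self-efficacy is not intake, and Aim 1b lists the two separately. The recall is the only intake measure described.

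**Step 4: look for a 26-week visit.** No section describes a follow-up or maintenance period, or any other 26-week assessment. The payment figures can be checked against the number of visits:

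- two visits: 2 × $20 = $40, leaving $52 − $40 = $12 for parking;
- three visits: 3 × $20 = $60, already $8 above $52 before any parking.

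The total fits two paid visits and not three. This is only indirect evidence, because the documents do not say that a recall requires a visit.

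**Step 5: check a straight-line reading.** With baseline and 26 weeks only, a model linear in time gives a 3-month change of 13.04 / 26 = 0.50 of the 26-week change, by assumption and not by measurement.

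**The case against.** The strongest reply is that 26 weeks is a leftover label and no data are at risk. Every other visit assessment is at baseline and post intervention, no 26-week visit is described, and the payments fit two visits. Other text also looks carried over from a different design: Aim 1 describes a single-arm trial while other sections randomise to two groups, and the sample size is 20 in one place and 40 in another. On that reading the remedy is a one-line correction, and the count of zero participants merely restates the literal schedule. This may well be right about intent. It does not remove the problem, because the recall sentence is the specific instruction to those collecting the data, and the general sentence about visits does not override it.

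Three narrower points stand:

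- The plan does not say how many recalls are taken at each time, so only the time points can be counted, not the recalls.
- Nothing says that dietary intake would drive the size of the later study. The effect on planning is possible, not certain.
- Dietary intake is one of many secondary outcomes. The primary BMD outcome and the feasibility outcomes under Aim 2 are unaffected.

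**Conclusion.** The concern holds. As written, the collection time and the analysis time for dietary intake contradict each other: about 13 weeks in the aims and the model, 26 weeks in the assessment schedule. Followed literally, the 3-month change in dietary intake is not estimable for any participant.

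The contradiction itself is certain, since it rests on the wording and a unit conversion. The loss of data is conditional on staff following the 26-week instruction. It also assumes that no unlisted 3-month recall is planned. The point that a 26-week value would mix in behaviour after the programme assumes that the programme ends with the 3-month trial period.

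This should be corrected before follow-up recalls are due. It is limited to one secondary outcome and does not threaten the trial's main result.

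**What to change.** Have the sponsor confirm the intended recall time, then make Specific Aims, Study Assessments and the statistical plan agree.

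1. **If 26 weeks is a labelling error**, replace it in Study Assessments with the 3-month post-intervention time. The cost is close to nil: participants already attend then, and the number of recall occasions is unchanged.
2. **If a 26-week follow-up is intended**, add a recall at 3 months for the planned analysis. Keep the 26-week recall as a separately labelled additional time point, outside the baseline-to-3-month model. The cost is at least one extra recall per participant, so at least 20 or 40 in total depending on which stated sample size applies.

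In either case, state how many recalls are taken at each time point and whether they are done at a visit, so that collection is uniform and the payment total can be checked.

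### The attendance-based efficacy estimate is named as an input for powering the next trial, with no statement that the intention-to-treat estimate governs (minor)

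*Combined protocol and SAP*

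**What the plan says.** Four statements in the Data Analytics and Statistical Plan matter here.

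- On the primary analyses: "All primary analyses will be performed using the intention-to-treat principle to estimate the effects of the program".
- On the additional analysis, the plan will estimate "intervention efficacy using as-treated analysis, where participants are classified according to the number of sessions actually attended (i.e. the dose-response will be evaluated").
- On purpose, the main focus is to "gather initial estimates on the effect sizes (group differences and intervention efficacy) to establish adequate statistical power for a future larger study".
- On power: "Given the sample size of 40 subjects, only large effect sizes will be detectable at 80% statistical power".

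The design that produces these estimates is described in more than one way. The Protocol Synopsis gives "Planned Sample Size: 20 subjects" and calls the study a randomised controlled trial. Specific Aims, Aim 1, says "We will conduct a single-arm clinical trial over 3 months". Study Assessments says that after baseline "they will be randomized to either the soccer group or the mobile health (mHealth) group". Sessions are described there for one arm only: "Participants in the soccer group will participate in soccer drills and other fitness routines (two 1-hour sessions per week").

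**The concern.** Within the analysis section, intervention efficacy is attached to the as-treated analysis. The same phrase then appears as one of two effect sizes meant to power the next trial. No sentence says that the ITT estimate takes precedence for that purpose; the ITT sentence covers only this study's primary analyses.

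Attendance is an outcome of the trial, not a baseline characteristic. Fitter or more motivated men may attend more and also change differently, so a contrast by sessions attended loses the protection of randomisation. Randomised trials are normally sized for the effect of assignment, and an attendance-based figure may differ from it in size or sign.

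The analysis is also not specified. It could be a slope or a set of categories, and it could use soccer men only or include mHealth men as zero sessions. At stake is the size of the next trial, and the plan calls gathering these effect sizes its primary focus.

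**Working it through.** **1. The plan's own power statement.** Inputs from the plan: two-sided 0.05, 80% power, 40 subjects, and a detectable effect described only as large. Allocation of 1:1 is assumed. Two arms: detectable effect = (1.960 + 0.842) × √(2/n per arm). One arm: (1.960 + 0.842)/√n, in SDs of change.

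| Design | Normal approximation | t-test |
|---|---|---|
| 20 + 20 | 2.802 × √(2/20) = 0.89 SD | 0.91 SD |
| 10 + 10 | 2.802 × √(2/10) = 1.25 SD | 1.32 SD |
| 20, single arm | 2.802/√20 = 0.63 SD of change | 0.66 |
| 40, single arm | 2.802/√40 = 0.44 SD of change | 0.45 |

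The word large fits a two-arm trial of 40. With 20 men randomised, the detectable effect is about 1.3 SD.

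**2. How far the attendance-based estimate could move.** None of these inputs is in the documents: true effect 0.30 SD, linear in attendance; attendance following Beta(7,3) (mean 70%) or Beta(18,2) (mean 90%); one health factor correlated 0.3 or 0.5 with attendance and, with either sign, with outcome change; no covariate adjustment. Slopes are multiplied by mean attendance, so the unconfounded target is 0.30. Each setting was simulated 30,000 times. Average estimates in SD, at 70% / 90% attendance:

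| Correlation with attendance, with change | Two-arm slope, mHealth = 0 (10 v 10) | Slope within 20 soccer men | High/low split, 20 soccer men |
|---|---|---|---|
| none | 0.30 / 0.30 | 0.30 / 0.30 | 0.09 / 0.03 |
| 0.3, 0.3 | 0.33 / 0.31 | 0.75 / 1.53 | 0.23 / 0.17 |
| 0.5, 0.5 | 0.38 / 0.33 | 1.56 / 3.72 | 0.48 / 0.42 |
| 0.3, −0.3 | 0.27 / 0.29 | −0.15 / −0.93 | −0.05 / −0.11 |
| 0.5, −0.5 | 0.22 / 0.27 | −0.96 / −3.12 | −0.29 / −0.35 |

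The two-arm slope is off by 0.01 to 0.08 SD, against a sampling SD of about 0.45 for the ITT estimate at 10 v 10. The within-soccer slope has an SD across trials of about 1.2 (70%) or 3.4 (90%) even without confounding, and 40% to 46% of its estimates have the wrong sign. Higher attendance makes it noisier, because less variation in attendance is left.

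The scale is a further unstated choice. Quoted at full instead of mean attendance, 0.30 becomes 0.30/0.70 = 0.43 or 0.30/0.90 = 0.33 SD without any confounding.

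**3. What that does to the next trial.** n per arm = 2 × (2.802/d)², two-sided 0.05, 80% power; the last column is the power if the true effect is 0.30 SD.

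| Planning value d | n per arm | Power |
|---|---|---|
| 0.30 | 175 | 80% |
| 0.22 | 325 | 97% |
| 0.31 | 164 | 78% |
| 0.38 | 109 | 60% |
| 0.75 | 28 | 20% |

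**4. Precision of the ITT estimate.** The 95% half-width is t(18) × √(2/10) = 2.101 × 0.447 = 0.94 SD at 10 per arm; 2.024 × 0.316 = 0.64 SD at 20 per arm; and 2.093/√20 = 0.47 SD of change for 20 men in one arm. With a true 0.30 SD, the chance of a wrong-sign estimate is Φ(−0.30/0.447) = 25% at 10 per arm and Φ(−0.30/0.316) = 17% at 20 per arm.

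**The case against.** The plan never says that the attendance figure will set the next sample size. It names group differences first, makes ITT primary, and leaves the choice open to the next protocol. Aim 2 also uses the word efficacy for something assessed by between-group differences, so the term is not reserved for the as-treated analysis. Under the two-arm reading the choice hardly matters: in the model above, the attendance slope and the ITT estimate correlate at 0.96 or higher, and their root mean square errors are about equal (0.44 against 0.45 in the most confounded setting). Age, smoking, alcohol use and therapy type are listed as possible covariates.

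Most of this stands, and it limits the point to a minor one. It does not remove it. The Aim 2 wording concerns engagement with physical activity; in the analysis section the phrase is tied to attendance and then reused for powering. If Aim 1 is single-arm, it yields no group difference in bone density, which leaves the attendance-based figure as the only one of the two named inputs that can be computed for the primary outcome. The covariates are optional, are not stated to apply to the as-treated analysis, and omit fitness and motivation.

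A reader might infer that the next trial would be grossly undersized, say 28 per arm instead of 175. The documents do not support that. Such figures need a slope fitted among soccer men and extrapolated to zero sessions, which the plan does not describe, together with assumed positive confounding. With confounding of the opposite sign, the error reverses.

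**Conclusion.** The point holds in a limited form and is minor. An estimate that can be confounded by self-selected attendance is named, without ranking, as an input for powering the next trial. The harm arises only if it is used that way. Under the stated assumptions the bias is about 0.01 to 0.08 SD either way in a two-arm slope with mHealth men at zero sessions, and possibly large, of either sign, in a comparison among soccer men. The documents do not choose between these readings, so neither the size nor the direction of the error can be derived from them. A reader might also infer that the as-treated analysis displaces ITT in this study; the plan says the opposite.

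The power statement needs correcting independently of those assumptions: 40 subjects conflicts with the planned 20, and the detectable effect differs accordingly (about 0.9 against 1.3 SD with 1:1 randomisation).

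**What to change.** - State that the effect size carried into the next sample-size calculation is the ITT estimate with its 95% confidence interval. If the trial is two-arm, this is the between-group difference. If single-arm, it is the pre-post change in all enrolled men, labelled as uncontrolled.
- Keep the dose-response analysis, call it exploratory instead of efficacy, and remove it from the powering inputs. Say whether attendance enters as a slope or as categories, and how mHealth men are classified.
- Reconcile single-arm (Aim 1) with randomised (Protocol Synopsis, Study Assessments), and 20 subjects (Protocol Synopsis, Aim 1) with 40 (Data Analytics and Statistical Plan). Then restate the detectable effect for the design and size chosen, using the table in the working.

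This costs a few sentences and needs no new data. The planning value may turn out less favourable. It also remains imprecise, with a half-width of about 0.94 SD at 10 per arm, so the interval must travel with the estimate. A single-arm pre-post change would still not be a between-group effect.
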